### **7.1 DEMOGRAPHIC AND OTHER BASELINE CHARACTERISTICS**

A table in the CTR will present the number of subjects screened, randomised and treated. The number of subjects prematurely discontinuing their study treatment will be shown with the reasons for discontinuation.

[figure not shown]
Descriptive statistics will be provided for demographics and baseline disease characteristics, presented by treatment group and overall total, based on the TS.

#### **7.1.1. Demographics**

- Age [years]
- Sex
- Race
- Ethnicity
- Country
- Region
- Weight [in kg]
- Height [in cm]
- BMI: Body mass index (BMI) [kg/m^2]: Weight [kg] / ( Height [m] × Height [m] )
- History of Cigarette Use (Never, Current, Former)
- Smoking Pack Years (continuous variable)
- Smoking Pack Years (<20, 20-40, >40)

#### **7.1.2. Baseline disease characteristics**

- Number of exacerbations requiring antibiotics in the past 12 months (categories [1,  $\geq$ 2] and [1, 2, 3,  $\geq$ 4])
- Treatment with cystic fibrosis transmembrane conductance regulator (CFTR) modulator therapy (yes vs no) based on concomitant therapy information
- *P. aeruginosa* status (positive vs negative) based on actual lab results

### **7.1.5. Baseline sputum assessment**

- Neutrophil Elastase in sputum (continuous variable and categorical: <25th percentile, 25th – 75th percentile, ≥75th percentile)
- NEATstik score
- Murray sputum colour

## **7.2 CONCOMITANT DISEASES AND MEDICATION**

Only descriptive statistics are planned for this section of the report.

Concomitant diagnosis and relevant medical history as well as non-drug therapies will be included as coded items using the current Medical Dictionary for Regulatory Activities (MedDRA) version in use at BI at the time of database lock. They will be summarized by MedDRA system organ class (SOC) and preferred term (PT) and will be descriptively presented by treatment group and overall total, based on TS. The CTR table will show the counts of patients with a Baseline condition in each SOC present (SOC sorted by standard European Medicines Agency [EMA] order) and then the conditions (PTs) under that SOC in descending order of overall prevalence.

Concomitant medication is defined as:

- Ongoing at the start of trial medication intake
- Starts within the on-treatment period (see CTP Section 6.2 for a definition of study phases)

Concomitant medications will be coded according to the most recent version of the World Health Organization – Drug Dictionary (WHO-DD) at the time of database lock. Concomitant medication use will be summarized by ATC and preferred name (PN) will use the ATC3 code, and will be sorted by alphabetical ATC class and decreasing frequency of PN in all patients within ATC class. Concomitant medications will cover the whole study duration and will be

presented by treatment group and overall total. Separate tables will be prepared for concomitant medications were ongoing at the start of trial medication intake, or started within the on-treatment period.

### **7.3 TREATMENT COMPLIANCE**

Only descriptive statistics are planned for this section of the report.

[figure not shown]
Treatment compliance (yes/no) will be based on the adherence to the expected range of 80-120% for the number of tablets actually taken vs. the number of tablets which should have been taken as directed by the investigator, see CTP Section 4.3. Number of subjects with or without treatment compliance will be summarized by treatment group per visit and overall.

### **7.4 PRIMARY OBJECTIVE ANALYSIS**

The primary objective is to estimate the number and percentage of patients who have at least one TEAE during the trial. The assessment will be performed on TS.

#### **7.4.1 Main analysis**

The main analysis is the same as safety analysis of patients who have at least one TEAE during the trial. Refer to [Section 7.8.1](#) for more details.

### **7.5 SECONDARY OBJECTIVE ANALYSIS**

#### **7.5.1 Key secondary objective analysis**

This section is not applicable as no key secondary endpoint has been specified in the protocol.

#### **7.5.2 Secondary objective analysis**

##### **7.5.2.1 Relative change from baseline in NE activity in sputum at Week 8 after first drug administration**

The analysis of this endpoint will be based on the TS and will be performed on log10-transformed data.

Baseline NE activity in sputum is defined as the mean value of Screening and Week 0 prior to the first treatment intake. Baseline NE activity will be summarized as continuous variable, as well as presented by categories as: <25th percentile, 25th-75th percentile, and >75th percentile.

Descriptive statistics for absolute NE activity on log10 transformed scale will also be presented by timepoint and treatment group.

### **% inhibition analyses**

The assessment of NE activity will further comprise the analysis of the % inhibition of NE activity. For the purpose of descriptive analysis, for each time point including baseline, % inhibition will be calculated as:

$$NE \ inhibition_t = \frac{NE \ activity_{baseline} - NE \ activity_t}{NE \ activity_{baseline}} \times 100$$

Descriptive statistics for absolute % inhibition by timepoint and treatment group will be presented. Maximum % inhibition (on patient level during the trial) will be summarized by treatment group. The median % inhibition of NE activity per treatment group over time will be plotted. All timepoints will be taken into account, analysis windows will be applied to the % inhibition of NE activity.

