7.2.4 Secondary objective analyses

7.2.4.1 Neutrophil elastase activity in sputum

The biomarker endpoint as described in [Section 2.1.3](#) will be analysed based on the TS. The analysis of this endpoint will be performed on log transformed data.

Baseline NE activity, in sputum, will be derived as the mean value of available valid samples of Screening and Week 0, prior to the first treatment intake. The change from baseline of NE activity, in sputum, at different visits (X) is calculated as:

[figure not shown]
Change from baseline in NE activity at Visit X = NE activity at Visit X – NE activity at Baseline

The change from baseline, in NE activity in sputum, at Week 8, will be analysed by descriptive statistics and graphical representations across all visits.

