7.5 DETERMINATION OF SAMPLE SIZE

For this exploratory trial, it is planned to include a total of 24 treated patients. Sixteen (16) patients will receive BI 1291583, 5 mg qd, and 8 patients will receive placebo. The planned sample size is not based on a power calculation but is considered sufficient, for the exploratory evaluation of safety, tolerability of BI 1291583, as well as to investigate PD and PK properties.

Apart from the safety assessment, NE inhibition, in sputum, is one of the main interests of the study to support further drug development decisions for BI 1291583. A variety of different effect sizes for % NE reduction were investigated, and [Table 7.5: 1](#) shows the simulated operating characteristics of the design for different scenarios and sample sizes for the active arm.

With 16 (24) patients in the active group, there is approximately 65% (70%) probability to observe a % reduction in NE activity, in sputum, of at least 80% when the true effect size is 90%. In contrast, if the true effect size is 40%, the probability to observe a % NE reduction of at least 80% would be 21%, for 16 patients in the active group, and 18% if there are 24 patients randomised, in the active group. If only 12 patients are evaluable for the assessment of % NE reduction at week 8 (e.g., due to dropouts) the increased uncertainty for a correct decision is considered acceptable.

Overall, a sample size of 16 patients, in the active group, is regarded as sufficient for the objectives of this trial.

Table 7.5: 1 Simulated probabilities for observing at least a given % reduction in NE activity, in sputum, at 8 weeks

Sample size	%Reduction	Probability to observe at least a 70% reduction (%)	Probability to observe at least an 80% reduction (%)	Probability to observe at least a 90% reduction (%)
12	95%	82.4%	75.5%	61.2%
	90%	70.0%	61.5%	45.4%
	80%	55.5%	45.7%	30.9%
	70%	45.7%	37.7%	22.6%
	50%	34.3%	25.9%	14.9%
	40%	30.1%	23.2%	12.4%
16	95%	86.9%	80.1%	64.2%
	90%	74.3%	64.7%	46.6%
	80%	57.7%	47.2%	29.5%
	70%	47.5%	36.7%	21.4%
	50%	34.4%	24.0%	12.8%
	40%	29.5%	21.1%	10.2%
24	95%	92.0%	86.0%	80.3%
	90%	80.3%	70.3%	48.4%
	80%	60.5%	47.9%	26.6%
	70%	47.8%	35.3%	17.3%
	50%	32.1%	21.2%	8.5%
	40%	26.8%	18.0%	6.9%

Assumptions: SD= 2.15 (on a log10 scale).

Simulations were performed using R Version 4.0.2, with 10000 simulation runs per scenario.

8. INFORMED CONSENT, TRIAL RECORDS, DATA PROTECTION, PUBLICATION POLICY, AND ADMINISTRATIVE STRUCTURE

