## **7. PLANNED ANALYSIS**

The labelling and display format of statistical parameters will follow BI standards (9.7). For End-Of-Text (EoT) tables, the set of summary statistics is: N / Mean / SD / Min / Median / Max. In descriptive statistics tables, mean, SD and median will be rounded to one additional digit than the raw individual value. In case extreme data outside of the expected range are observed, quartiles and percentiles will be presented additionally.

Tabulations of frequencies for categorical data will include all possible categories and will display the number of observations in a category as well as the percentage (%) relative to the respective treatment group (unless otherwise specified, all subjects in the respective subject set whether they have non-missing values or not). The category missing will be displayed only if there are actually missing values.

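### The SAP's default table prints an arithmetic mean and SD of raw % NE inhibition, two columns that mislead under the plan's own SD; the Week 8 estimate is not named

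*SAP*

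**What the plan says.** The secondary endpoint is the relative change from baseline in sputum NE activity at Week 8. Protocol 7.2.4.1 puts the analysis on log-transformed data and defines "Change from baseline in NE activity at Visit X" as a simple difference from baseline. SAP 5.2.2.1 uses log10 values and refers to SAP 7.5.2.1 for how the relative change is estimated.

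SAP 7.5.2.1 then lists several displays:

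- absolute NE activity on the log10 scale;
- % inhibition, computed per patient on the raw scale as (baseline - value) / baseline x 100;
- change from baseline in log10 NE activity.

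For % inhibition it says "Descriptive statistics for absolute % inhibition by timepoint and treatment group will be presented", and it plots the median over time. For End-Of-Text tables, SAP section 7 fixes the default: "the set of summary statistics is: N / Mean / SD / Min / Median / Max". Quartiles and percentiles are added to that set, not substituted, if extreme values appear.

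Protocol 7.5 gives the assumed spread, "SD= 2.15 (on a log10 scale", and the arm sizes: "Sixteen (16) patients will receive BI 1291583, 5 mg qd, and 8 patients will receive placebo".

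**The concern.** The endpoint is named as a relative change, and the only percentage that the visible text defines is the raw per-patient ratio. That ratio is bounded above and unbounded below. One patient with a 100-fold rise contributes 100 x (1 - 100) = -9,900%. If the other 15 patients each show exactly 90% inhibition, the arm mean is (15 x 90 - 9,900) / 16 = -534%.

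Protocol 7.5 names NE inhibition in sputum as a main interest for development decisions, and Protocol 5.4.1.2 intends a comparison with non-CF bronchiectasis data. A reader may find a large negative mean beside a median near 89%, with nothing to say which one answers the endpoint. For PK, Protocol 7.2.4.2 adds the geometric mean and geometric CV. For NE, whose assumed spread is very wide, the visible text has no counterpart.

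**Working it through.** **Inputs.** SD 2.15 on the log10 scale, 16 active and 8 placebo patients, and the scenario "when the true effect size is 90"% (Protocol 7.5). A 90% reduction is a mean log10 change of log10(0.10) = -1. SDs of 0.93 and 0.5, and the caps on rises, are assumptions of this review, used to show the range.

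**Model.** Per-patient log10 change d ~ Normal(-1, 2.15²); % inhibition = 100 x (1 - 10^d).

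**Step 1: reproduce the plan's figure.** Protocol 7.5 states: "With 16 (24) patients in the active group, there is approximately 65% (70%) probability" of observing at least an 80% reduction. The n=16, true 90% row of Table 7.5: 1 reads:

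| | at least 70% | at least 80% | at least 90% |
|---|---|---|---|
| Table 7.5: 1 | 74.3 | 64.7 | 46.6 |
| Simulated, median of raw % reductions | 74.3 | 64.9 | 46.8 |

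Across the whole table the raw median falls within 2 points in 53 of 54 cells. The back-transformed mean log10 change does so in 17 of 54 (about 71% for the 64.7% cell). The arithmetic mean of raw % reductions does so in none (0.3% for that cell). So 2.15 behaves as the SD of per-patient change, and the plan's operating characteristics describe the raw median.

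**Step 2: why the mean fails.** The chance that one patient rises at least 10-fold is P(Z > (1 + 1)/2.15) = P(Z > 0.93), about 17.6%. That is 16 x 0.176 = 2.8 expected patients, each contributing -900% or worse. The lognormal expectation of the mean is 100 x [1 - 0.1 x exp((2.15 x ln 10)²/2)], about -2.1 million %. This is driven by extreme tails, so the typical (median) trial result is the fairer measure.

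**Step 3: the mean in a typical trial** (n=16, true 90%, 200,000 simulated trials):

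| Setting | Typical arithmetic mean | P(mean < 0) |
|---|---|---|
| SD 2.15, unbounded lognormal | about -4,200% | 96% |
| SD 2.15, rises capped at 100-fold (assumed) | about -1,040% | 96% |
| SD 2.15, rises capped at 10-fold (assumed) | about -130% | 93% |
| SD 0.93 (assumed) | about 43% | 26% |
| SD 0.5 (assumed) | about 82% | about 0 |

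At SD 2.15 without a cap, the typical sample SD is about 13,000 percentage points. In a placebo arm of 8 with no effect, the mean is negative in 98% of trials, so the sign of this column hardly separates the arms.

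**Step 4: the other statistics on the same data.** The sample median is typically about 89% at SD 2.15 and about 90% at the smaller SDs. The back-transformed mean log10 change is typically 90% at every SD. Its 95% sampling range at SD 2.15 comes from -1 ± 1.96 x 2.15/√16 = -1 ± 1.05, which is about -13% to 99% on the percentage scale.

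**The case against.** The strongest reply is that the plan already shows a sound percentage. The median is in the same default set, it is the statistic plotted over time, and it is the one that reproduces Table 7.5: 1. The change from baseline is also summarised on the log10 scale, and % inhibition is introduced as a further display. All of this stands. A reader might infer that the plan will report a negative effect, that the mean is the decision statistic, or that the endpoint analysis as a whole is wrong. The documents support none of these: no section gives the mean priority, and two of the planned summaries are robust.

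The size can also be challenged. The -4,200% needs an unbounded lognormal tail. A finite assay range would shorten that tail, and setting values below quantification to half the limit (SAP 6.6) puts a floor under individual baseline samples and so limits some rises. The documents give neither the assay range nor the limit. This is why the capped results are shown: the magnitude falls sharply, but at SD 2.15 the mean is still usually negative.

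Finally, parts of the SAP are redacted, so a back-transformation may be specified in text that cannot be checked. That weakens the point about the unnamed estimate. It does not affect the mean and SD columns, which follow from visible text.

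**Conclusion.** The concern holds for two columns and one omission. The arithmetic mean and SD of raw % inhibition are planned. Under the sponsor's own SD, with 16 active patients and a true 90% reduction, they mislead: the mean is typically between about -130% (10-fold cap, assumed) and about -4,200% (no cap), and negative in 93% to 96% of trials. At SD 0.5, an assumed value, the mean is about 82%, a modest understatement of 90%. The median and the log10 summaries are unaffected. The omission is that the visible text does not identify the statistic that is the Week 8 relative change. The result rests on the stated SD being that of per-patient change, which the match with Table 7.5: 1 supports, and on approximate lognormality. For an exploratory secondary endpoint this is an inexpensive improvement, not a flaw that undermines the trial.

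**What to change.** In SAP 7.5.2.1, name the Week 8 estimate. The preferred form is 100 x (1 - 10^(mean change in log10 NE)) per arm, with a 95% CI back-transformed in the same way and labelled exploratory; Protocol 7.1 already allows for such intervals. For raw % inhibition, present the median, quartiles and range, and leave out the arithmetic mean and SD.

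Naming the raw median as the estimate is an acceptable alternative and has the advantage of matching Table 7.5: 1. An active/placebo ratio is optional, given a descriptive plan and 8 placebo patients.

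The cost is SAP wording and one table shell, with no new data. There are two downsides. The raw % inhibition table would depart from the SAP's default set of statistics. The interval would also be wide: with an observed mean log10 change of -1 and SD 2.15, a t interval is -1 ± 2.131 x 2.15/√16 = -1 ± 1.145, or about -40% to 99%. That width is a property of the assumed spread and is better shown than hidden.

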### **Change from baseline analyses**

Change from baseline in log10-transformed NE activity in sputum up to Week 12 after first drug administration will be analysed by descriptive statistics and graphical representations across all visits. Descriptive statistics of change from baseline will be presented by timepoint and treatment group.

#### 7.5.2.2 Pharmacokinetic endpoints

[figure not shown]
The analyses of PK parameters  $AUC_{\tau}$ ,  $C_{max}$ ,  $AUC_{\tau,ss}$  and  $C_{max,ss}$  are performed according to (9.8) based on the PKS.  $AUC_{\tau}$  and  $C_{max}$  for the first dose as well as at steady state ( $AUC_{\tau,ss}$  and  $C_{max,ss}$ ) will be summarized for the active treatment group.

**Boehringer Ingelheim**  
**TRIAL STATISTICAL ANALYSIS PLAN**  
**1397-0013**

**Page 25 of 37**

**c44359225-01**

Proprietary confidential information © 2024 Boehringer Ingelheim International GmbH or one or more of its affiliated companies.

## **7.7 EXTENT OF EXPOSURE**

The date of first drug administration is recorded at Visit 2 (Day 1). The following parameters will be calculated to assess extend of exposure:

Duration of exposure [months] = (date of last administration – date of first administration +1 day) / 30.5

Duration of exposure in categories:  $\leq 1$  months (31 days);  $> 1$  months (31 days) to  $\leq 2$  months (62 days);  $> 2$  months (62 days) to  $\leq 3$  months (91 days)

Total dose [mg]: Duration of exposure [days]  $\times$  actual dose [mg]

Finally, first dose and last dose administration, and the reason for premature treatment discontinuation will be listed for each subject.

## **7.8 SAFETY ANALYSIS**

All safety analyses will be presented by randomised treatment and overall total, based on the TS.

### **7.8.1 Adverse Events**

Unless otherwise specified, the analyses of AEs will be descriptive in nature. All analyses of AEs will be based on the number of subjects with AEs and NOT on the number of AEs.

The analysis of AEs will be based on the concept of TEAEs. All AEs occurring between first drug intake and end of REP, a period of 28 days after the last drug intake will be assigned to the on-treatment period for evaluation. All AEs occurring before first drug intake will be assigned to ‘screening’ and all AEs occurring after last drug intake + REP of 28 days will be assigned to ‘follow-up’ (for listings only). For details on the treatment definition, see [Section 6.1.1](#).

According to ICH E3 ([9.9](#)), ‘other significant’ AEs need to be listed in the clinical trial report. These will be any non-serious AE that led to an “action taken = study drug withdrawn”.

[figure not shown]
An overall summary of TEAEs will be presented by treatment group. In addition, the following displays will be provided:

- Patients with any AE
- Patients with AEs by worst intensity
- Patients with severe AEs
- Patients with serious AEs (reason for seriousness included as per CRF)
- Patients with investigator reported drug-related AEs
- Patients with AEs leading to death
- Patients with adverse events of special interest
- Patients with AEs leading to discontinuation of study treatment
- Patients with other significant AEs

The frequency of subjects with AEs will be summarized by treatment, primary SOC and PT (MedDRA version used will be displayed in the tables).

The SOC will be presented in descending frequency of the total number of AEs for each system organ class in all patients. The PTs within each SOC will be ordered by descending prevalence in all patients. Cases with multiple occurrences of the same PT will be counted only once under that PT. Patients with AEs in several PTs within the same SOC will be counted only once at the SOC level.

Proprietary confidential information © 2024 Boehringer Ingelheim International GmbH or one or more of its affiliated companies.

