7.2.3 Primary objective analyses

The primary endpoint as described in [Section 2.1.2](#), will be derived according to BI standards. The analysis will be based on the TS and will be descriptive in nature. The number and proportion of patients, with at least one TEAE per treatment group, will be derived. TEAE is defined as all adverse events occurring between the start of treatment and the end of the REP (see [Section 1.2](#)). Adverse events that start before first drug intake and deteriorate under treatment will also be considered as ‘treatment-emergent’.

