7.2.6 Safety analyses

All treated patients will be included in the safety analysis. In general, the safety analyses will be descriptive in nature and will be based on BI standards. No hypothesis testing is planned.

Adverse events will be coded using the Medical Dictionary for Drug Regulatory Activities (MedDRA). Standard BI summary tables and listings will be produced. All adverse events with an onset between the start of treatment and the end of the REP, a period of 28 days after the last dose of trial medication, will be assigned to the on-treatment period for evaluation.

Statistical analysis and reporting of AEs will concentrate on TEAEs (see [Section 7.2.3](#)).

Frequency, severity, and causal relationship of adverse events will be tabulated by system organ class and preferred term, after coding according to the current version of the Medical Dictionary for Drug Regulatory Activities (MedDRA), at database lock.

Laboratory data will be analysed both quantitatively as well as qualitatively. The latter will be done via comparison of laboratory data to their reference ranges. Values outside of the reference range, as well as values defined as clinically relevant, will be summarised.

Vital signs, physical examinations, or other safety-relevant data observed at screening, baseline, during the course of the trial, and at the end-of-trial evaluation, will be assessed with regard to possible changes compared with findings before start of treatment.

Clinically relevant abnormal findings of ECG will be reported and analysed as baseline conditions (at screening) or as AEs (during the trial).

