## **5. ENDPOINTS**

### **5.1 PRIMARY ENDPOINT(S)**

The primary endpoint is the occurrence of any treatment-emergent adverse event (TEAE), up to 16 weeks after first drug administration. Details on the concept of TEAE are described in [Section 7.8.1](#).

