5.2.2.2 Pharmacokinetic endpoints

The following pharmacokinetic endpoints are assessed for BI 1291583 5 mg only.

- AUC $\tau$ : AUC (area under the curve) over a dosing interval for the first dose
- Cmax: maximum concentration for the first dose
- AUC $\tau$ ,ss: AUC $\tau$  at steady state after multiple dosing of BI 1291583 5 mg qd
- Cmax,ss: Cmax at steady state after multiple dosing of BI 1291583 5 mg qd

Proprietary confidential information © 2024 Boehringer Ingelheim International GmbH or one or more of its affiliated companies.

Pharmacokinetic endpoints from the population PK analysis and/or Population PK/PD analysis will be defined in the Population PK Analysis Plan. Refer to Section 7.2.4.2 of the CTP for details of the analyses of the pharmacokinetic endpoints.

[figure not shown]

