## 6. GENERAL ANALYSIS DEFINITIONS

### 6.1 TREATMENT(S)

#### 6.1.1 Analysis phases

For safety analyses, data collected between first drug intake up to the end of residual effect period (REP) will be considered as “on-treatment” period for the evaluation.

Table 6.1.1: 1 Analysis phases

Study analysis phase	Label	Start (included)	End (excluded)
Screening	Screening	Date of informed consent at 12 a.m.	Date/time of first drug administration
Treatment	Placebo BI 5 mg respectively	Date/time of first administration of study drug	12:00 a.m. on day after last drug administration, or 12:00 a.m. on day after last contact date (whichever occurs first)
Residual effect period	Residual effect period	12:00 a.m. on day after last administration of study drug	12:00 a.m. on day after last administration of study drug + REP (28 days)
Follow-up 	Follow-up	12:00 a.m. on day after last administration of study drug + REP (28 days)	12:00 a.m. on day after last contact date

 This phase exists only in those subjects whose last contact date is more than 28 days after last trial drug administration.

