Analysis of AE data (including findings in 12-lead ECG assessments or physical examinations), potentially clinically significant abnormal laboratory values, concomitant medication or non-drug therapies will not be based on visits and thus no assignment to time windows is necessary. For this type of data, a safety analysis ‘on-treatment’ concept will be used depending on their actual onset dates.

Table 6.7: 2 Time windows for assignment of safety assessment – laboratory

[figure not shown]
Visit number (CTP)	Visit label (analysis)	Planned Day	Time window [days]		
			Window per CTP	Start (analysis)	End (analysis)
V1	Screening	-42	≥7d prior to V2	All pre-baseline measurements	
V2	Baseline	1	± 0	NA	Date/time of first administration of study drug
V3	Week 1	8	± 3	Start of on-treatment phase 	18
V4	Week 4	29	± 3	19	43
V5	Week 8	57	± 3	44	71
V6	Week 12	85	± 3	72	End of on-treatment phase 
EoS	Follow-up	113	+ 7	All post-treatment measurements after last drug intake + REP	

 As defined in [table 6.1.1: 1](#).

Table 6.7: 3 Time windows for assignment of biomarkers assessed in sputum

Visit number (CTP)	Visit label (analysis)	Planned Day	Time window [days]		
			Window per CTP	Start (analysis)	End (analysis)
V1	Screening	-42	≥7d prior to V2	All pre-baseline measurements	
V2	Baseline	1	± 0	NA	Date/time of first administration of study drug
V3	Week 1	8	± 3	Start of on-treatment phase 	18
V4	Week 4	29	± 3	19	43
V5	Week 8	57	± 3	44	71
V6	Week 12	85	± 3	72	Last drug administration
EoS	Safety Follow-up	Last drug administration + 28		All measurements after last drug administration + 1	All measurements before last drug administration + 36

 As defined in [table 6.1.1: 1](#).

Proprietary confidential information © 2024 Boehringer Ingelheim International GmbH or one or more of its affiliated companies.

For all variables with a sparse sampling schedule that does not match the schedules in the above tables, the screening, baseline and follow-up phase will follow the same rules, while the start and end days of the on-treatment time windows will be equidistant from the planned visit day.

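### The visible SAP rule files every AE that begins before first intake under screening, whereas the protocol counts such an AE as treatment-emergent if it worsens on treatment (minor)

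*SAP*

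**What the plan says.** **Protocol.** Section 7.2.3 defines TEAEs in two parts. The first is timing: AEs occurring from the start of treatment to the end of the residual effect period (REP). The second is worsening: "Adverse events that start before first drug intake and deteriorate under treatment will also be considered" treatment-emergent. Section 7.2.6 has its own onset-based sentence for the on-treatment period, but then says "Statistical analysis and reporting of AEs will concentrate on TEAEs" and points back to 7.2.3, so the second part stays in force.

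**SAP.** Section 5.1 states the primary endpoint and adds "Details on the concept of TEAE are described in" Section 7.8.1. Section 7.4.1 says "The main analysis is the same as safety analysis of patients who have at least one TEAE during the trial", again referring to 7.8.1. Section 7.8.1 assigns AEs from first intake to 28 days after last intake to the on-treatment period, and then says "All AEs occurring before first drug intake will be assigned to" screening. The phase table in 6.1.1, to which 7.8.1 refers, starts the screening phase at "Date of informed consent at 12 a.m" and ends it at first dose. For AE data, Section 6.7 says that the on-treatment "concept will be used depending on their actual onset dates". None of these places mentions worsening.

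**The concern.** The SAP's own links for the primary endpoint run from 5.1 and 7.4.1 to 7.8.1, and from there to the phase table in 6.1.1. A programmer who follows them never meets the protocol's worsening rule, and does meet a sentence that covers all pre-dose AEs without exception. For the PK endpoints, by contrast, SAP 5.2.2.2 sends the reader to the protocol: "Refer to Section 7.2.4.2 of the CTP for details of the analyses of the pharmacokinetic endpoints".

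Pre-dose AEs can be in the database, because Protocol 5.2.6.2.1 collects AEs from informed consent onwards. At stake is whether a patient whose screening AE gets worse on study drug is counted in the primary endpoint of a trial whose primary objective is safety and tolerability.

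**Working it through.** The plan gives no expected TEAE rate, so there is no figure to reproduce. The check compares the two rules case by case and then sizes one discrepant patient.

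**Step 1: where the rules differ.** Take a treated patient and ask whether each rule counts that patient as having at least one TEAE.

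| Patient's AEs | Protocol 7.2.3 | SAP 7.8.1 read literally |
|---|---|---|
| Any AE with onset from first intake to end of REP | counted | counted |
| Screening AE that worsens, with the worsening entered as a new AE with post-dose onset | counted | counted |
| Screening AE that worsens and keeps its original onset date; no other AE with onset from first intake to end of REP | counted | **not counted** |
| Only screening AEs, none worsening | not counted | not counted |

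The rules part company in the third row only. Every patient whom the SAP counts is also counted by the protocol, so literal use of the SAP can leave the count in an arm unchanged or lower it, but cannot raise it.

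**Step 2: can the third row occur?** Protocol 5.2.6.1.1 requires worsening of pre-existing conditions to be recorded. It does not say whether a worsened screening AE becomes a new record with its own onset date or stays as one record with a changed intensity. The documents leave this open, and it decides whether the third row can be populated.

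**Step 3: size per affected patient.** Planned group sizes from Protocol 7.5 are 16 on active and 8 on placebo, 24 in total. The shift per missed patient is 1/n:

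- active: 1/16 = 6.25 percentage points;
- placebo: 1/8 = 12.5 percentage points;
- overall column (SAP 7.8 presents an overall total): 1/24 = 4.2 percentage points.

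The difference in proportions, active minus placebo, falls by 6.25 points for a patient missed on active and rises by 12.5 points for one missed on placebo. Its direction therefore depends on where such patients fall, which is unknown.

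**Step 4: what cannot be computed.** The documents give neither the frequency of worsening screening AEs nor the proportion of patients with no other on-treatment AE. No expected number of affected patients is claimed.

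**The case against.** The strongest case on the other side is that the SAP inherits the protocol rule. SAP 3 takes the protocol as read and states that the plan rests on Section 7 of the protocol, which contains 7.2.3. SAP 7.8.1 opens by basing the AE analysis on the TEAE concept, and its next sentences can be read as assigning AEs to phases without redefining the term. Protocol 7.2.6 likewise sets an onset-based sentence beside a reference to TEAEs. SAP 6.7 is chiefly about visit windows.

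Much of this stands. It makes an unintended omission the likeliest explanation. It does not remove the conflict, because Protocol 7.2.6 refers back to 7.2.3 whereas SAP 5.1 names 7.8.1 as the place where the TEAE concept is set out, and the visible 7.8.1 speaks of all pre-dose AEs.

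A second objection is that the rule may exist out of sight. The SAP contents list puts 7.8.1 on page 27 and 7.8.2 on page 29, so part of 7.8.1 has probably been redacted. Only 4.2 is visible in SAP Section 4, and Protocol 7.2.3 also relies on sponsor standards. This stands too: the point can be made only about the visible text, and the redaction is not itself a fault.

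A third is that the discrepant case is narrow: a screening AE that worsens, is not re-entered, and belongs to a patient with no other on-treatment AE. That is correct, and it limits the severity.

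A reader might infer that the sponsor has deliberately narrowed the primary endpoint, or that TEAEs will be under-reported in favour of the active arm. The documents support neither. No visible text declares a change of definition, and nothing shows that affected patients exist or in which arm they would be.

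**Conclusion.** The concern holds as a minor conflict between the visible texts. Followed literally, the SAP misses a patient whose only qualifying event is a worsened screening AE kept under its original onset date, although the protocol counts that patient. The conclusion assumes that no redacted passage or sponsor standard supplies the rule and that the eCRF does not always turn worsening into a new AE. If either assumption fails, the count is unaffected, though the sentence in 7.8.1 would still need a qualification or cross-reference. The sizes in Step 3 assume that the treated set matches the planned 16 and 8. The endpoint is descriptive and Protocol 7.1 rules out confirmatory testing, so nothing inferential changes.

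**What to change.** Before treatment information is released (SAP 8):

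1. In SAP 7.8.1, qualify the sentence on pre-dose AEs: an AE with onset before first intake that deteriorates during the on-treatment period counts as treatment-emergent, citing Protocol 7.2.3. Take the period from SAP 6.1.1, which for safety analyses runs from first intake to the end of the REP; Protocol 7.2.3 does not itself give a window for the worsening.
2. Add the matching exception to the onset-date sentence in SAP 6.7.
3. Confirm whether the eCRF records worsening as an intensity change or as a new AE, and state in the SAP which of these identifies a worsened AE.

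If redacted text or a sponsor standard already holds the rule, a cross-reference in 7.8.1 is enough. If the narrower definition is intended, declare it as a change from the protocol.

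The cost is one derivation line, one clause and one check of the eCRF completion rule, with no protocol amendment. If the eCRF captures worsening in neither form, a short site instruction or data query is needed before database lock.
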